9.7.2 Primary Efficacy Variables

The primary efficacy measure will be the plasma FVIII activity monitored on a regular basis after BMN 270 dose. The efficacy goal of the protocol is to ascertain the dose range of BMN 270 required to convert severe HA patients to expression of FVIII at 5 IU/dL or above, (ie, a mild severity). This is associated in natural history studies with clinically superior long term outcomes (Den Ujil, 2011, Haemophilia).

The following assays (assessed by the central laboratory) will be used to measure the primary efficacy variable:

- FVIII activity (chromogenic substrate assay)
- FVIII activity by one-stage clotting assay

If a subject has used FVIII within 72 hours of a measurement day, all efforts should be made to obtain FVIII activity measurements when a 72-hour interval without FVIII use is achieved.

270-201 Amendment 8

The 72-hour wash-out period is only intended for subjects who have achieved FVIII ≥ 5 IU/dL at 16 weeks after BMN 270 infusion and who have not resumed standard of care FVIII replacement therapy.

The FVIII activity level in both assays and the number of subjects with FVIII activity ≥ 5 IU/dL in at least one of the two assays will be summarized.

FVIII activity assays will also be performed at the local laboratory at the time points indicated in Table 9.1.2, Table 9.1.3, Table 9.1.4, and Table 9.1.5 but will be used in conjunction with local lab LT assessments to monitor subject safety and need for initiation of therapeutic corticosteroid dosing; local laboratory FVIII activity assessments will not be used to assess efficacy or to measure the primary efficacy outcome of the study.

Subjects who do not respond to BMN 270 treatment (ie, treatment failure, manifesting as either failure to achieve FVIII activity ≥ 5 IU/dL by Week 52 or inability to maintain independence from prophylactic FVIII replacement therapy due to joint bleeding episodes, in the judgment of the Investigator) may, at the Investigator's discretion and after discussion with the Medical Monitor, follow an abbreviated visit schedule after Week 52, as applicable and at the discretion of the Investigator.

Timing of assessment by these assays is provided in Table 9.1.2, Table 9.1.3, Table 9.1.4, and Table 9.1.5. Details on performing the assays are included in the Laboratory Manual.

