Subjects who consent should have their FVIII levels monitored/adjusted by the Investigator to enable the procedure to be performed safely. This may require the administration of exogenous FVIII replacement products in order to achieve the desired FVIII activity. The target FVIII activity level within 24 hours prior to the liver biopsy is at the discretion of the Investigator and/or according to local guidelines, but at a minimum should be at the lower limit of the normal range (ie, at least 50 IU/dL).

Table 9.1.7 presents the schedule of assessments for participation in the liver biopsy substudy.

270-201 Amendment 8

	Pri	BMN 270		
Assessment	Screening ⁱ (Day -28 to Day -1)	Smart Rescreening ⁱ (Day -28 to Day -1)	Baseline (Day -7 to Day -1) ^h	Infusion Visit (Day 1) ^k
Informed consent	X			, , ,
Medical History	Х			
Physical Examination ^a	Х		Х	Х
Height and Weight ^a	X			
Vital Signs	Х	Х		Х
Assessment of Adverse Events and Concomitant Medications	Х	X	Х	Х
Documentation of bleeding episodes and FVIII usage (by either subject or clinical information)	X	Х	Х	
Distribution of subject diaries and training in their use			Х	
Electrocardiogram	Х			
Chest X-ray	X			
Liver Ultrasound	X			
hFVIII Assays ^b	X	Xj		
AAV5 Assays ^c	Х	X		Х
Screen for Hepatitis B, Hepatitis C, HIV ^d	Х			
Blood chemistry, haematology, coagulation screen, and CRPe	Х	Х	Х	
Urine Tests ^e	Х	X	Х	
Liver Tests ^e	Х	Х	Х	
PBMC collection for CTL baseline			Х	
Von Willebrand Factor Antigen (VWF:Ag)	Х			
Direct Thrombin Test			Х	
PCR of vector DNA in blood, saliva, urine, semen, and stools			Х	
Biomarker testing ^f	Х			
Exploratory biomarker assessments ^g			Х	
Haemo-QoL-A Quality of Life (QoL) assessment			Х	
BMN 270 Infusion				Х

Table 9.1.1: Schedule of Events – Screening and Infusion

Proprietary and Confidential

31 January 2019

270-201 Amendment 8

- ^a Complete physical examination should be done at Screening. Brief physical examination may be done at Baseline and at the BMN 270 Infusion Visit. Height will be recorded at Screening only. Weight will be recorded at Screening and then every 6 months thereafter.
- ^b Includes baseline hFVIII activity (chromogenic substrate assay and one-stage clotting assay), hFVIII coagulation activity exploratory assay, hFVIII inhibitor level (Bethesda assay with Nijmegen modification), hFVIII total antibody titer, and hFVIII antigen (ELISA).

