9.4.8.1 Concomitant Haemophilia Treatments

Subjects on "on demand" therapy for FVIII will continue their treatment at will. Subjects on prophylactic FVIII therapy will discontinue their treatment starting the day of infusion and switch to an "on demand" schedule. FVIII can always be taken as needed by the subject, who will carefully record his treatment and bleeding episodes in his diary. In addition, information on FVIII usage by medical history will be collected (if available) from subjects for the 6 month period immediately preceding study enrollment.

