12.5.1 Once per week (Weeks 1 through 16)

The following procedures will be performed at one visit per week from Weeks 1 through 16:

- Physical examination
- Assessment of Adverse Events and Concomitant Medications (including review of subject diary for bleeding and FVIII use)
- Vital Signs
- Liver Tests (refer to Table 9.7.8.3.1) central laboratory assessment
 - LTs may be monitored more or less frequently (and in particular when ALT values are >1.5x ULN) based on discussion between the Medical Monitor and the Investigator and review of subject data.
- Samples for FVIII Assays central laboratory assessment
 - FVIII activity level (one-stage clotting assay)
 - FVIII activity level (chromogenic substrate assay)
 - FVIII coagulation activity exploratory assay
 - o Bethesda assay (with Nijmegen modification) for hFVIII inhibitor level
 - FVIII antigen (ELISA)

Note: If a subject has used FVIII within 72 hours of a measurement day, all efforts should be made to obtain FVIII activity measurements when a 72-hour interval without FVIII use is achieved. The 72-hour wash-out period is only intended for

subjects who have achieved FVIII \geq 5 IU/dL at 16 weeks after BMN 270 infusion and who have not resumed standard of care FVIII replacement therapy.

- Central assessment of FVIII activity level should be performed 1x/week from Week 1 through Week 16
- Liver Tests (refer to Table 9.7.8.3.1) local laboratory assessment
 - LTs may be monitored more or less frequently (and in particular when ALT values are >1.5x ULN) based on discussion between the Medical Monitor and the Investigator and review of subject data.
- FVIII activity level local laboratory assessment
 - FVIII activity level (one-stage clotting assay)
 - FVIII activity level (chromogenic substrate assay)
- PBMC collection

12.5.2 Week 1 – Day 2 and Day 4

On Day 2 and Day 4 of Week 1, the following procedures will be performed:

- PCR of vector DNA in blood, saliva, urine, semen, and stools (Day 2 and Day 4)
- Samples for FVIII Assays (Day 4 only) central laboratory assessment
 - FVIII activity level (one-stage clotting assay)
 - FVIII activity level (chromogenic substrate assay)
 - FVIII coagulation activity exploratory assay
 - o Bethesda assay (with Nijmegen modification) for hFVIII inhibitor level
 - o FVIII antigen (ELISA)

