14.2 Primary and Secondary Efficacy Analysis

The subjects will be followed in a longitudinal manner and all the relevant information will be collected. The analysis of the data will be descriptive in nature. Descriptive statistics include the number of subjects, mean, median, standard deviation, minimum, and maximum for continuous variables and count and percent for categorical variables. Efficacy variables will be summarized by dose cohort at each time point. Relationship between dose and efficacy results will be examined.

Data collected in a longitudinal manner may be analyzed using longitudinal methods such as mixed effect model which takes into account the correlation among the observation taken at various time points within a participant. Efficacy is a secondary endpoint, defined as biologically active hFVIII at ≥ 5 IU/dL by chromogenic substrate assay and/or one-stage clotting assay as measured by the central laboratory at 16 weeks following study treatment. hFVIII activity will be assessed weekly during the study period. We can only assess the true steady state of hFVIII protein produced from BMN 270 after a minimum of 72 hours has elapsed since the last infusion of FVIII protein concentrates.

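### The 72-hour FVIII wash-out is conditioned on the Week-16 response it should protect and contradicts Section 14.2, so infused FVIII can count as response

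*Protocol*

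**What the plan says.** Section 9.7.2 opens with a best-effort instruction that applies to everyone: "If a subject has used FVIII within 72 hours of a measurement day, all efforts should be made" to obtain the activity measurement after a 72-hour FVIII-free interval. It then narrows this: "The 72-hour wash-out period is only intended for subjects who have achieved FVIII" of 5 IU/dL or more "at 16 weeks after BMN 270 infusion and who have not resumed standard of care FVIII replacement therapy". Both conditions must hold.

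The same restriction stands in the FVIII-assay footnotes of Tables 9.1.2 to 9.1.5 and in the visit procedures of Section 12. Section 12.5.1, which covers Weeks 1 to 16, carries it ("The 72-hour wash-out period is only intended for" the same group) beside the instruction "Central assessment of FVIII activity level should be performed 1x/week from Week 1 through Week 16". Section 12.5.2 applies it even to Day 4.

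Section 14.2 states the validity condition with no restriction by subject, counting from the most recent FVIII concentrate: "We can only assess the true steady state of hFVIII protein produced from BMN 270 after a minimum of 72 hours has elapsed".

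Three other provisions matter. Section 9.4.8.1 lets subjects take FVIII on demand at any time. Section 9.7.2 counts a subject as reaching 5 IU/dL if either assay does. No text in the protocol removes a recently infused value, or a subject back on replacement, from that count.

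**The concern.** The rule is circular. Whether the wash-out applies to a subject depends on his Week-16 activity, which is the measurement the wash-out should keep clean. Before Week 16 nobody can satisfy the condition, so on its face it covers neither the Week 3 readings that drive escalation in Cohorts 1-3 nor the Week 8 readings that drive expansion of Cohort 4. After Week 16 it leaves out the non-achievers, who are the likeliest to be infusing FVIII.

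The trial aims to relate dose to activity of at least 5 IU/dL at Week 16. Infused FVIII biases only upward, so the error is a false responder. It is most likely where expression is low, which means the lower doses and the true non-responders. That flattens the dose relationship the trial is meant to describe.

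**Working it through.** The protocol gives no power or error-rate figure here, so there is nothing to reproduce. The check has a textual part and a size part.

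**Text.** Section 14.2 makes 72 h a requirement for reading expression in any subject. Section 9.7.2 says the 72 h is not meant for subjects below 5 IU/dL at Week 16 or for those back on FVIII. For those subjects both statements cannot hold.

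**Inputs from the protocol.**
- Half-life of FVIII: about 8-12 h (Section 7) and 12-18 h (Section 7.3).
- Bleeds on demand: up to 30-50 a year (Section 7.3); at least 12 in the past year for on-demand entrants (Section 9.3.1).
- Cohort size: up to 4 in Cohorts 1-3, up to 3 + 3 = 6 in Cohort 4 (Section 9.1).

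**Assumptions.** The protocol gives no post-infusion peak, so P = 30, 50 or 100 IU/dL is assumed, with one-compartment decay. Bleeds follow a Poisson process with one infusion each. Repeat infusions would raise the chances below; a working transgene would lower them.

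**Hours that infused FVIII alone stays at or above 5 IU/dL:** T = h × log2(P/5).

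| Peak P (IU/dL) | h = 8 h | h = 12 h | h = 18 h |
|---|---|---|---|
| 30 | 20.7 | 31.0 | 46.5 |
| 50 | 26.6 | 39.9 | 59.8 |
| 100 | 34.6 | 51.9 | 77.8 |

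At 24 h with a 12 h half-life the residual is P × 2^(-2) = 7.5, 12.5 or 25 IU/dL. Each passes the cut-off with no transgene product.

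**Chance that a visit falls within 72 h of an infusion:** 1 - exp(-r × 72/8760).
- r = 12 a year: 9.4%
- r = 30: 21.9%
- r = 50: 33.7%

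Not every such value would reach 5 IU/dL on infused FVIII alone. In the middle case (P = 50, h = 12), only an infusion in the last 39.9 h does so, and the chances become 5.3%, 12.8% and 20.4%.

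**Effect on the count.** One false responder moves the rate by 1/6 = 17 points in a cohort of six and 1/4 = 25 points in a cohort of four.

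**What a 72 h rule achieves.** The residual at 72 h is P × 2^(-72/h). For P = 50 it is 0.1, 0.8 and 3.1 IU/dL at half-lives of 8, 12 and 18 h. For P = 100 it is 0.2, 1.6 and 6.3. At 18 h the peak must stay below 5 × 2^4 = 80 IU/dL for the residual to fall under 5. So 72 h removes most of the contamination, but not all of it in the extreme case.

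**Baseline (secondary).** Table 9.1.1, footnote b, places the baseline sample at Screening ("Includes baseline hFVIII activity (chromogenic substrate assay and one-stage clotting assay") with no wash-out note, while "Subjects on prophylactic FVIII therapy will discontinue their treatment starting the day of infusion". With evenly spaced prophylaxis at the protocol's 2-4 infusions a week, the chance that a Screening sample falls within 72 h of one is 72/84 = 86% at two a week. It is 100% at three or four, where the spacing is 56 h or less.

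**The case against.** The best defence is that this is a drafting slip with limited reach. The Amendment 6 rationale says the aim was to exempt subjects who had resumed standard-of-care FVIII, so the Week-16 clause looks unintended. A subject who reads 5 IU/dL or more at Week 16 without having resumed FVIII does fall in the wash-out group, and the best-effort instruction then applies to him. A contaminated value below 5 is still a correct non-response. The analysis is descriptive, individual activity plots over 16 weeks are planned, and Section 14.9 lets the SAP prevail on discrepancies.

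Much of this stands, and it limits the harm. It does not remove the contradiction. A best effort neither requires a repeat sample nor excludes the contaminated value, and subjects back on FVIII stay in the count. The sentence also tells sites when to draw blood, and an SAP cannot recover a clean sample that was never sought.

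A reader might infer four stronger things that the documents do not support:
- **Rescheduling can never rescue Week 16.** With a visit window of ±48 h, this holds only for an infusion less than 72 - 48 = 24 h before the planned time. Extra FVIII testing is also allowed in any study week.
- **Contaminated baseline values distort the response count.** The cut-off is absolute, and severity at entry rests on medical history and base level. Before dosing there is no transgene product to confuse with infused FVIII. Only the PD parameter C_b and comparisons with baseline are affected, and the cause is a missing Screening instruction, not the sentence in Section 9.7.2.
- **30-50 bleeds a year is typical.** The protocol gives it as an upper range.
- **False responders have occurred.** The text shows only that they can.

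**Conclusion.** The concern holds. The wash-out rule in Section 9.7.2, the footnotes and Section 12 is circular, cannot be applied in Weeks 1-15, and contradicts Section 14.2. This is a fault in what the protocol states, not detail left to the SAP. Followed as written, it allows infused FVIII to be counted as a Week-16 response.

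The exposure is about 9% of visits within 72 h of an infusion at the entry minimum of 12 bleeds a year, rising to 22-34% at the upper range, with infused activity alone above the cut-off for 21-78 h. These figures rest on the assumed peaks and on one infusion per bleed. Where expression is high the response status will rarely change: Section 7.3.1 reports mean activity above 50 IU/dL in the second year. The risk sits with low doses and non-responders, in cohorts where a single subject moves the rate by 17-25 points.

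**What to change.** 1. Reconcile Section 9.7.2, the footnotes of Tables 9.1.2-9.1.5 and Section 12 with Section 14.2. Delete the Week-16-achievement condition, and tie the validity of an activity value to time since last exogenous FVIII, for every subject.
2. Exclude central values drawn within 72 h of recorded FVIII use from the Week-16 responder count and the PD summaries.
3. Report the number of subjects without a valid Week-16 value, including those back on FVIII, separately and without imputation, in line with Section 14.1.2.
4. As a secondary step, flag Screening values drawn within 72 h of FVIII and leave them out of the C_b summaries. Do not substitute a value.

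This governs which values are analysed; no FVIII treatment is withheld. Amendment 7 records that all subjects have already been screened, so baseline can be corrected only in analysis, but sampling in Years 2-5 still carries the restriction and can be changed. The cost is wording and programming. A few values are lost, the responder count may fall slightly, and infusion times are needed as well as dates.

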9.7.3 Secondary Efficacy Variables

Secondary efficacy measures will be the reduction in the frequency of factor replacement therapy, and reduction in the number of bleeding episodes. Subjects will be asked at each study visit to report the use of factor replacement therapy and the number of bleeding episodes since the previous visit. This information will be captured on the subject's diary or other subject records.

In subjects who experience recurrent bleeding episodes, the Investigator and Medical Monitor will discuss whether to resume prior FVIII prophylaxis.

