Treatment of severe HA presently consists of intravenous injection of plasma derived or recombinant human FVIII protein (rhFVIII) concentrates both as prophylaxis 2-4 times per week, and at the time of a bleed, to prevent or control bleeding episodes, respectively. The half-life for FVIII (12-18 hours for most approved products) necessitates frequent infusions, and although a major advance in the treatment of HA, it remains common for severe HA patients to continue to have multiple bleeding events on treatment (mean of 1 to 7 episodes/year with prophylaxis and up to 30 to 50 episodes/year for on demand treatment) (Nagel, 2011, Haemophilia.). The consequence of multiple bleeding events is the development of an underlying pathology that contributes to debilitating multiple-joint arthropathy and substantially increased risk of death (Nagel, 2011, Haemophilia). Chemical modification (eg, direct conjugation of polyethylene glycol (PEG) polymers) and bioengineering of FVIII (eg, FVIII-Fc fusion proteins) improve half-life by approximately 50%, and thus, show promise in reduced dosing and maintaining activity levels above 1% trough (Stonebraker, 2010, Haemophilia.), (Mahlangu, 2014, Blood). However, these longer acting FVIIIs remain dependent on multiple infusions to maintain critical levels of FVIII activity in severe HA patients. There is therefore a strong unmet need for a fully preventive treatment of HA to give patients a FVIII level compatible with a normal and haemorrhage-free life.

Proprietary and Confidential

270-201 Amendment 8

[figure not shown]
Page 29

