8 STUDY OBJECTIVES

The primary objectives of the study are:

- To assess the safety of a single intravenous administration of a recombinant AAV5 encoding human coagulation FVIII (AAV5-hFVIII-SQ) vector.
- To determine the dose of AAV5-hFVIII-SQ required to achieve expression of hFVIII at or above 5% of normal activity (≥5 IU/dL) at 16 weeks after infusion. The kinetics, duration and magnitude of AAV-mediated hFVIII activity in individuals with haemophilia A will be determined and correlated to an appropriate BMN 270 dose.

The secondary objectives of the study are:

- To describe the immune response to the hFVIII transgene product and AAV capsid proteins following systemic administration of AAV5-hFVIII-SQ
- To assess the impact of BMN 270 on the frequency of FVIII replacement therapy during the study
- To assess the impact of BMN 270 on the number of bleeding episodes requiring treatment during the study

The exploratory objectives of the liver biopsy substudy are:

- To examine the histopathology of the liver following BMN 270 therapy, including assessing for possible safety findings (eg, fibrosis, fatty liver disease, lymphocytic invasion)
- To quantify FVIII DNA, RNA, and protein expression within hepatocytes
- To determine which forms of rAAV genomic DNA (eg, concatemers) are present at the time of biopsy
- To determine the transduction pattern in humans (ie, peri-portal hepatocytes, central vein hepatocytes)

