9.2 Discussion of Study Design, Including Choice of Control Group

Study 270-201 is designed to be a first-in-man, phase 1/2 open-label, dose escalation study in patients with severe haemophilia A. Four doses of BMN 270 will be evaluated and the dose escalation decision tree for Cohorts 1-3 is summarized in Figure 9.1.1.

The decision to escalate to the next dose level will be made based on the review of safety parameters and FVIII activity by the Sponsor and the DRB.

There will be no control group. Parameters for each subject will be compared to a pre-treatment assessment of safety (liver function) and efficacy (number of bleeds, use of replacement therapy).

As AAV based treatment always leads to anti-capsid immune response, no true control group (for example with an empty AAV) is possible.

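### In subjects who enter on prophylaxis, the change in FVIII replacement frequency is confounded by the protocol's own stop of prophylaxis and can show a substantial fall with no vector effect

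*Protocol*

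**What the plan says.** Section 8 of the protocol (Amendment 8) lists as a secondary objective "To assess the impact of BMN 270 on the frequency of FVIII replacement therapy during the study". Section 9.7.3 turns this into a variable: "Secondary efficacy measures will be the reduction in the frequency of factor replacement therapy, and reduction in the number of bleeding episodes". Section 9.2 sets the comparator: there is no control group, and number of bleeds and use of replacement therapy are each compared with the subject's own pre-treatment assessment.

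Section 9.4.8.1 fixes what happens to background treatment: "Subjects on prophylactic FVIII therapy will discontinue their treatment starting the day of infusion and switch to an" on-demand schedule. It adds that "FVIII can always be taken as needed by the subject". Under Section 9.7.3, if bleeding recurs, "the Investigator and Medical Monitor will discuss whether to resume prior FVIII prophylaxis".

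Patients on prophylaxis are eligible: the minimum bleed count in inclusion criterion 3 (Section 9.3.1) does not apply to them. Section 14.2 makes the analysis descriptive, summarises efficacy by dose cohort at each time point and looks at the relation between dose and efficacy. None of these sections separates subjects by prior regimen, or scheduled infusions from infusions given for a bleed.

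**The concern.** For a subject who enters on prophylaxis, the period before infusion contains scheduled doses and the period after contains none unless prophylaxis is resumed. That difference is assigned on Day 1, before anyone knows whether the vector expresses FVIII. With no control group undergoing the same stop, the before/after contrast cannot tell the removal of scheduled infusions from an effect of BMN 270, although the objective attributes the change to BMN 270.

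If the vector fails, the two secondary measures can move in opposite directions: infusions fall because prophylaxis was withdrawn, and bleeds rise for the same reason. Read alone, the first would look like benefit.

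The problem also reaches the dose comparison. Cohorts are very small (up to four subjects in Cohorts 1-3, three plus a possible three in Cohort 4). If prophylaxis and on-demand subjects are mixed unevenly across them, the mix of prior regimens alone could create or hide a dose trend in FVIII use.

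**Working it through.** The protocol states no expected reduction, so there is no figure to reproduce. The check asks what the measure would show in a prior-prophylaxis subject if the vector did nothing.

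**Inputs**
- Scheduled infusions: f = 2 to 4 per week (Section 7.3), so 52 × f = 104 to 208 per year.
- Bleeds: "mean of 1 to 7 episodes/year with prophylaxis and up to 30 to 50 episodes/year for on demand treatment" (Section 7.3). So b_p = 1 to 7 per year on prophylaxis and b_o = 30 to 50 on demand.
- Infusions per treated bleed, k: not in the protocol. Assumed, and shown for 1 to 4.

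**Formulas**
- Before: 52f + b_p·k infusions per year.
- After, inert vector, no resumption: b_o·k.
- Apparent reduction: 1 − b_o·k / (52f + b_p·k).
- Break-even: k = 52f / (b_o − b_p).

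**Results** over the 12 combinations of f (2, 3, 4), b_p (1, 7) and b_o (30, 50):

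| k (assumed) | Smallest reduction (f=2, b_p=1, b_o=50) | Largest reduction (f=4, b_p=7, b_o=30) | Combinations with no reduction |
|---|---|---|---|
| 1 | 1 − 50/105 = 52% | 1 − 30/215 = 86% | 0 of 12 |
| 2 | 1 − 100/106 = 6% | 1 − 60/222 = 73% | 0 of 12 |
| 3 | 1 − 150/107 = −40% (an increase) | 1 − 90/229 = 61% | 2 of 12 |
| 4 | 1 − 200/108 = −85% (an increase) | 1 − 120/236 = 49% | 5 of 12 |

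Break-even k runs from 104/(50 − 1) = 2.1 to 208/(30 − 7) = 9.0. The 30 to 50 bleeds are upper figures in the protocol; a lower on-demand rate would make the artefact larger.

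**Resumption.** If prior prophylaxis is restored at week T of a horizon of H weeks, the reduction scales by T/H. With T = 16 and k = 1:
- H = 52: 52.4% × 16/52 = 16% and 86.0% × 16/52 = 26.5%, about 16-27%.
- H = 260: 52.4% × 16/260 = 3% and 86.0% × 16/260 = 5%.

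**The paired measure.** Under the same null, bleeds would rise between 30/7 = 4.3-fold and 50/1 = 50-fold.

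**The case against.** A reader might infer that this endpoint is bound to be met, with a large reduction, in every prophylaxis subject. The documents do not support that.

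- **Nothing is there to be met.** Section 14.2 is descriptive, Section 14.7 has no power calculation, and no success threshold is stated.
- **Size and sign depend on a number the protocol does not give.** On-demand infusions count as replacement therapy. At three or more per bleed, an inert vector could leave total use unchanged or higher in some combinations.
- **Resumption is provided for.** Recurrent bleeding, which an inert vector would produce, prompts a discussion of returning to prior prophylaxis. That dilutes the artefact heavily over long follow-up.
- **Other measures would expose failure.** Bleed reduction stands in the same sentence of Section 9.7.3. The primary efficacy measure is central-laboratory FVIII activity (Section 9.7.2). Being unable to stay off prophylaxis because of joint bleeds already counts as treatment failure (Sections 9.1, 9.7.2 and 12.8). It would also go too far to infer that the plan reads a fall in FVIII use as efficacy regardless of bleeding; no passage says so.
- **The SAP may split the tables by regimen.** It is not shown, and Section 14.9 lets it prevail.

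These points limit the claim without removing it. Resumption is only to be discussed, and it shrinks the artefact without changing its sign; a summary of FVIII use at Week 16 would carry the whole of it in anyone who had not resumed. That bleeds and FVIII use would diverge confirms that FVIII use cannot be read alone, yet Section 8 makes it an objective in its own right. A descriptive summary of a confounded contrast can still mislead. The variable, the comparator and the mandated stop are all fixed in the protocol, so this is not a detail merely left to the SAP.

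**Conclusion.** The concern holds for subjects who enter on prophylaxis. In them, the change in total FVIII frequency against their own earlier use is confounded by the mandated stop and cannot be read as an effect of BMN 270. With an inert vector and no resumption, the apparent fall is 52-86% at one infusion per bleed and 6-73% at two; at three or more it can vanish or reverse. Resumption at Week 16 reduces the 52-86% to 16-27% over 52 weeks and 3-5% over 260 weeks.

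These figures rest on the general rates in Section 7.3, not on data from the enrolled subjects, and on the assumed infusions per bleed. The before/after total in subjects treated on demand at entry is not affected by the stop, because their regimen does not change.

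Because the measure is secondary and descriptive and drives no stated escalation or stopping rule, this should be corrected but is not critical to the trial.

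**What to change.** In Sections 9.7.3 and 14.2:

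1. Report FVIII use separately by regimen at entry (prophylaxis, on demand) and by reason for infusion (prophylaxis, bleed treatment, surgery/procedure), before and after BMN 270.
2. For prior-prophylaxis subjects, take as efficacy measures (a) annualised FVIII used to treat bleeds, before versus after, and (b) time on study without resumed prophylaxis. Withdrawing prophylaxis pushes (a) up rather than down: at one infusion per bleed, from 1-7 to 30-50 per year under the null. The stop therefore cannot produce a false fall. Measure (b) matches the independence from prophylaxis that the protocol already uses in defining treatment failure.
3. For these subjects, show total FVIII use only beside the bleed rate, labelled as including the protocol-mandated stop.
4. Keep the before/after total for on-demand subjects.

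No treatment rule changes. The cost is some wording, one extra table and a smaller headline reduction in FVIII use. Section 9.7.7.1 shows that the FVIII infusion eCRF pages carry at least one reason category, for surgery or procedures; whether they carry the others should be confirmed. The pre-study history covers six months and is collected only if available (Section 9.4.8.1), so measure (a) will be missing before treatment where the reason for infusion was not recorded.
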